Adverse Event	Date of Onset dd/mmm/yyyy	Outcome 1=Resolved 2=Resolved w/Sequelae 3=Ongoing 4=Unknown	Date of Resolution dd/mmm/yyyy (If <24 hrs, please indicate Hrs/Mins)	Intensity 1=Mild 2=Moderate 3=Severe	Action taken w/Study Device Tx 1=None 2=Reduced 3=Interrupted 4=Discontinued	Relationship to Study Device 1=Not Related 2=Unlikely Related 3=Possibly Related 4=Probably Related 5=Related	Serious AE? 1=No 2=Yes (If Yes, Complete SAE/UADE Form)	Unanticipated AE? 1=No 2=Yes

PI Signature (at end of clinical trial): _____

Date: _____

Protocol: A Non-Invasive Neuromodulation Device for Prevention of Episodic Migraine Headache
Adverse Events/Adverse Device Effects

SUBJECT ID: _____

SITE #: _____

PROTOCOL NUMBER: _____

Please check the box, if the subject **did not** experience any AEs/Adverse Device Effects (ADEs) during the study. _____ (Initial/Date)

Adverse Event	Date of Onset dd/mmm/yyyy	Outcome 1=Resolved 2=Resolved w/Sequelae 3=Ongoing 4=Unknown	Date of Resolution dd/mmm/yyyy <small>(If <24 hrs, please indicate Hrs/Mins)</small>	Intensity 1=Mild 2=Moderate 3=Severe	Action taken w/Study Device Tx 1=None 2=Reduced 3=Interrupted 4=Discontinued	Relationship to Study Device 1=Not Related 2=Unlikely Related 3=Possibly Related 4=Probably Related 5=Related	Serious AE? 1=No 2=Yes <small>(If Yes, Complete SAE/UADE Form)</small>	Unanticipated AE? 1=No 2=Yes

PI Signature (at end of clinical trial): _____

Date: _____

SUBJECT ID: _____
DATE: _____SITE #: _____
PROTOCOL NUMBER: _____**Serious Adverse Event (SAE)/ Unanticipated Adverse Device Effect (UADE)**

Adverse Event (AE) Term:			
Event Start Date (dd/mmm/yyyy)	_____ / _____ / _____	Event End Date (dd/mmm/yyyy)	_____ / _____ / _____
Is the event still ongoing?		 Yes	 No
Type of Report:  Initial  Follow up  Final			

Demographics with no personal identifiers:

Date of Birth: _____ / _____ / _____	 Male	 Female
--------------------------------------	-------------------------------	---------------------------------

Serious Criteria: (check all that apply)	
 Inpatient hospitalization or prolongation of hospitalization Date of Hospitalization _____ / _____ / _____ Date of Discharge _____ / _____ / _____	
 Immediately Life Threatening (immediate risk of death)	
 Persistent or significant disability/incapacity	
 Congenital anomaly/Birth defect	
 Other important medical event which required an intervention to prevent permanent impairment	
 Death Date of Death _____ / _____ / _____	

	Yes	No
Was the AE unanticipated (unexpected)?		
Was the AE caused by, or associated with the investigational device?		
Did the event improve or disappear after stopping device treatment?		
Is there a relationship of the event to any other suspect cause?		

SUBJECT ID: _____
DATE: _____

SITE #: _____
PROTOCOL NUMBER: _____

Serious Adverse Event (SAE)/ Unanticipated Adverse Device Effect (UADE)

Briefly describe the presentation and clinical course, including medical treatment, of the event: (attach additional pages, if needed)

Please Note: For device clinical trials, investigators are required to submit a report of SAE/UADE to the sponsor and reviewing IRB as soon as possible, but no later than **10 working days** after the investigator first learns of the event (21 CFR 812.150(a)(1)). However, if the SAE/UADE involves a death it must be reported within **24 hours** of discovery. Any follow-up information will be submitted to the sponsor and IRB as soon as the relevant information is available.

Signature/Date of person completing form: _____

Signature/Date of Principal Investigator: _____

Connecting your new Scion Trials email account to a smartphone or tablet

This guide is in two sections. The first section covers Apple iPhones and iPads, and the second section covers Android smartphones and tablets.

Section 1: Apple iPhones and iPads

[figure not shown]
Adding security to your iPhone or iPad

We ask that you set a passcode on the iPhone or iPad that you plan to use which, once set, will need to be entered when you turn on the iPhone or iPad. It is possible that you already have a passcode set. If you do not, follow these steps to add one:

1. Go to the main screen of the iPhone or iPad that shows all of your icons and tap on the Settings icon.
2. Go down to Touch ID & Passcode and tap on it, or it might just say Passcode depending on the model of iPhone or iPad that you have.

[figure not shown]
3. Tap turn passcode on.

4. Enter a passcode and re-enter it to confirm when prompted to do so. Remember what you set as the passcode, because you will need to enter it each time you want to use your device.

[figure not shown]
Connecting your iPhone or iPad to your new Scion Trials email account

1. Go to the App Store and search for the Gmail app. If you locate it correctly, the title of the app show as “Gmail – email from Google” as shown below. Tap GET to download it and enter the password for your Apple ID if prompted to complete the download. If you see the word OPEN next to the app listing then you already have the Gmail app on your device.

[figure not shown]

2. Open the app and enter your new Scion Trials email address when prompted. The app should bring you to the inbox for the email account.

[figure not shown]
3a. To write a new email on the **iPhone** version of the app, tap on the red box icon that has a pencil inside it at the top right corner of the inbox.

3b. To write a new email on the **iPad** version of the app, tap on the red box icon that has a pencil inside it above the inbox.

4. When you have finished writing the email, tap on the blue arrow at the top right corner to send the message:

[figure not shown]
Section 2: Android smartphones and tablets

Since there are so many different types of Android smartphones and tablets, this guide will describe the general steps involved. It is possible that this guide may exactly reflect the screens you see, but if not you should see general similarities on your screens.

[figure not shown]
Adding security to your Android smartphone or tablet

We ask that you set a passcode on the Android smartphone or tablet that you plan to use which, once set, will need to be entered when you turn on the smartphone or tablet in the future. It is possible that you already have a passcode set. If you do not, follow these steps to add one:

1. Go to the settings on your Android smartphone or tablet and tap on Security. Then tap on Screen lock.

[figure not shown]
2. Tap on PIN to make a numeric code.

[figure not shown]
3. Enter the PIN code that you want to use and re-enter it if prompted to do so. Remember what you set as your PIN because you will need it in the future when you turn on your device.

Connecting your Android smartphone or tablet to your new Scion Trials email account

1. Go to the settings on your Android smartphone or table and tap on the Add Account setting.

[figure not shown]

2. In the next screen tap on Google.

3. In the next Add a Google Account screen if you are asked whether you want to create a new account or use an existing account, tap Existing. Then type your Scion Trials email address and password when prompted to do so.

4. If you then see a screen asking you what you want to sync for this email account, only put a check mark next to Gmail. Clear the other check marks.

That's it! If you have any questions, please contact us at [contact].

Protocol: A Non-Invasive Neuromodulation Device for Prevention of Episodic Migraine Headache

Sponsor: Scion NeuroStim, LLC (SNS)

Schedule of Visits and Procedures

Procedures	Screening Visit	Baseline Period (28 days; weeks 1-4)	Treatment Day 1 Week 5	Clinic Visit Day (week 7; check on treatment experience)	Phone Contact Week 9	Phone Contact Week 11	Phone Contact Week 13	Phone Contact Week 15
Informed Consent	X							
Inclusion/Exclusion criteria	X							
Headache History Questionnaire	X							
Medical History	X							
Medication Usage (Concomitant Medication)	X		X	X	X	X	X	X
Ear Exam (presence of cerumen)	X		X	X				
Vital Signs (height & weight)	X		X	X				
Device Treatment Training			X	X				
Device Treatment at Research Site			X	X				
Usability Questionnaire			X	X				
Train/Review Daily Headache Diary	X	X	X	X	X	X	X	X
Quality of Life Questionnaires (HIT-6, Pittsburgh Sleep, BDI-II, BAI)			X					
Urine Pregnancy Test			X					
Randomization			X					
Dispense CVS Device			X					
Collect Treatment Data from CVS-M Device								
Return CVS Device								
Adverse Event Reporting	X	X	X	X	X	X	X	X

Protocol: A Non-Invasive Neuromodulation Device for Prevention of Episodic Migraine Headache

Sponsor: Scion NeuroStim, LLC (SNS)

Schedule of Visits and Procedures

Procedures	Final Visit for Initial Tx Period (end of week 16); Also Initiation of 2nd Tx period	Phone Contact Week 18	Phone Contact Week 20	Phone Contact Week 22	Phone Contact Week 24	Phone Contact Week 26	Final Visit for 2nd Tx Period; end of Tx (end of week 28); Start of Observation Period
Informed Consent							
Inclusion/Exclusion Criteria							
Headache History Questionnaire							
Medical History							
Medication Usage (Concomitant Medication)	X	X	X	X	X	X	X
Ear Exam (presence of cerumen)	X						X
Vital Signs (height & weight)	X						X
Device Treatment Training							
Device Treatment at Research Site	X						
Usability Questionnaire	X						X
Train/Review Daily Headache Diary	X	X	X	X	X	X	X
Quality of Life Questionnaires	X						X
Urine Pregnancy Test	X						
Randomization							
Dispense CVS-M Device	New treatment cards for all subjects						
Collect Treatment Data from CVS-M Device	X						X
Return CVS Device							X
Adverse Event Reporting	X	X	X	X	X	X	X

Protocol: A Non-Invasive Neuromodulation Device for Prevention of Episodic Migraine Headache**Sponsor:** Scion NeuroStim, LLC (SNS)**Schedule of Visits and Procedures**

Procedures	Phone Contact Week 30	Phone Contact Week 32	Phone Contact Week 34	Phone Contact Week 36	Phone Contact Week 38	Final Study visit (end of week 40) Or Early Termination Visit
Informed Consent						
Inclusion/Exclusion Criteria						
Headache History Questionnaire						
Medical History						
Medication Usage(Concomitant Medicatio	X	X	X	X	X	X
Ear Exam (presence of cerumen)						X
Vital Signs (height & weight)						X
Device Treatment Training						
Device Treatment at Research Site						
Usability Questionnaire						
Train/Review Daily Headache Diary	X	X	X	X	X	
Quality of Life Questionnaires						X
Urine Pregnancy Test						
Randomization						
Dispense CVS-M Device						
Collect Treatment Data from CVS-M Device						
Return CVS Device						
Adverse Event Reporting	X	X	X	X	X	X

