- have a cochlear implant
- have chronic tinnitus
- have temporomandibular joint disease
- have been diagnosed with traumatic brain injury
- have been diagnosed with neurological disease other than headaches

- have a diagnosed vestibular dysfunction and/or balance dysfunction
- have a history of abusing alcohol or other drugs
- are experiencing medication overuse headaches (individuals with respect to whom the principal investigator is concerned that analgesic abuse is involved based on the ICHD-II guidelines).
- are less than 18 years old or greater than 65 years old
- have had eye surgery within the previous three months or ear surgery within the previous six months
- have active ear infections or a perforated tympanic membrane
- have participated in another clinical trial within the last 30 days or are currently enrolled in another clinical trial
- are using Botulinum toxin-based treatments for migraines or for facial cosmetic reasons.
- are taking anti-emetics chronically (more than 2 times per week, consistently)
- Though not excluded, subjects taking anti-histamines will be encouraged not to take such medications within four hours prior to a CVS treatment. The investigator should review other medications taken by the subject with properties that mimic anti-nausea or anti-dizziness drugs as these may reduce responsiveness of the vestibular system to caloric stimulation. Such medications should also be avoided within four hours prior to a CVS treatment.

- **Withdrawal Criteria**

- Subjects must be withdrawn from the clinical trial if any of the following events occur:
 - Surgery during the study period.
 - A subject does not continue to meet inclusion/exclusion criteria.
 - A subject is significantly non-compliant with the requirements of the protocol (principal investigator & sponsor decision).
 - The subject does not complete at least 25 of 28 daily diary entries in her/his headache diary during the baseline period. (That is, the subject must be compliant with maintaining the headache diary.)
 - A subject becomes pregnant during the trial as evidenced by a positive pregnancy test.
 - The subject develops an illness (adverse event) that would interfere with his/her continued participation.
 - The subject withdraws his/her consent.
 - The principal investigator feels that it is the subject's best interest to be withdrawn.
 - Scion Neurostim discontinues the study or has achieved the targeted enrollment.

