Note: The treatment delivery data (recorded on the SD cards) from the CVS device consists of temperature waveform files that contain actual measured temperature values that were delivered to the earpieces during treatments. This data is an independent record of the expected device performance and is used for confirmation purposes only. The SD card data files also record treatment times and subject compliance, which will be used to calculate the level of treatment compliance. Subjects will *not* be informed that the device monitors treatment compliance.

- **End of Second Treatment Period – Start of Observation Period:** At the end of the second treatment period, all subjects will return their devices to the clinics. The SD cards will be collected. Subjects will be asked to complete the QOL questionnaires again and will be asked to complete a final usability questionnaire.

Subjects will then be asked to continue to make recordings in their headache diaries for an additional 12 weeks.

- **End of Observation Period/End of Study:** Subjects will return to the clinics one final time. They will be asked to complete the QOL questionnaires.

5) Active Treatment Parameters; Placebo Treatments

The following parameters will be set for active treatments using the CVS device:

- A standardized CVS time-varying waveform lasting approximately 19 minutes will be used for all active treatment subjects at all study sites. Treatments will be administered once or twice daily, based upon a subject's randomization assignment. The two daily treatments should ideally be separated by at least one hour.
- The waveform schedule for active treatment subjects will consist of a warm sawtooth delivered to one ear and a cold sawtooth delivered to the other ear. The warm sawtooth will go from body temperature to 42 °C, and the cold sawtooth will go from body temperature to 17 °C. The two waveforms will be delivered simultaneously, but will have different oscillation frequencies. After each two-day period, the warm and cold waveforms will be switched so that the opposite ears will be treated with the different caloric stimulation. Thus every two days the ear receiving the cold stimulus will be switched to the warm stimulus and vice versa.

The following parameters will be set for the placebo treatments using the CVS-M Device:

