An experienced, independent and blinded Statistician will analyze and summarize the daily headache diaries for all subjects and evaluate the primary endpoint and observational aims. A blinded reviewer will analyze and summarize the quality of life data.

The primary aim of this trial is to determine if subjects randomized to the twice-daily active group, have a greater reduction in the number of headache days than those assigned to the twice-daily placebo group. For this study, the reduction in headache days (primary endpoint) is calculated as the number of headache days during the baseline month minus the number of headache days during treatment month three. An intent-to-treat methodology will be employed for the primary aim; however, per protocol analyses will also be conducted for comparison. Analysis of the primary endpoint and the secondary headache-related endpoints assessed in the daily diary will be performed for all subjects that complete at least 25 diary entries or more during the relevant 28-day treatment month. Treatment compliance is defined as completion of at least 50% during

each treatment months (for the per protocol evaluation). Subjects with treatment compliance below 50% during any treatment month will be assigned to the intent-to-treat group only. As accurate assessment of some of the secondary endpoints assessed during study period do not depend on daily headache diary compliance, treatment compliance will be the only criteria for inclusion in the per protocol analysis of those secondary outcomes. Statistical significance will be defined with a Type I error of 5% ($\alpha=0.05$). Wilcoxon rank-sum tests (for non-normal data) or a paired student's t-tests (for normal data) will be used to establish whether the reductions in headache days between the baseline and third treatment month in each treatment arm are statistically significant. Mann-Whitney U tests (for non-normal data) or unpaired student's t-tests (for normal data) will be used to determine whether the reduction in migraine headaches in the twice daily active treatment arm subjects is significantly greater than that observed in the twice daily placebo treatment arm subjects. No interim analyses of efficacy are planned.

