BAI (completed)			

BDI-II scores above 20 or **BAI** scores above 16 after treatment has commenced should be referred to the PI for consultation with [name]. If the subject answers in the affirmative to question 9 of the BDI-II form, he/she should be referred for mental health counseling on that same clinic visit.

SUBJECT ID: _____
DATE: _____SITE #: _____
PROTOCOL NUMBER: _____**Device Treatment at the Clinical Site with new Treatment Card:****Yes No**

Was a new Treatment Card (SD card) inserted into the device before treatment?	Yes	No
Any side effects or AEs reported after device treatment?	Yes	No
Was the device treatment aborted?	Yes	No
Any complaints from subject?	Yes	No
Any concerns about the subject?	Yes	No
If Yes, to any questions above, please provide comment:		

- Review device compliance and proper operation of the device and delivery of treatments.
- Administer Usability Questionnaire after completion of device training.
- Review Daily Headache Diary completion and upload to gmail account each day.
- Collect and return old Treatment card (SD card) from the device to Scion NeuroStim (SNS).

I have reviewed the data from this visit and found the information to be complete and accurate. I verify that all of the tasks have been performed.

Principal Investigator Signature

Date

SUBJECT ID: _____
DATE: _____SITE #: _____
PROTOCOL NUMBER: _____**Phone Contact (Week 18)****A phone call to the subject is required every 2 weeks after Initiation of 2nd Treatment Period**

Date of this phone contact	____	/	____	/	____
----------------------------	------	---	------	---	------

Adverse Events and Concomitant Medication Assessment:	Yes	No
Any Adverse Events (AEs) since last visit?		
If Yes, please complete AE form.		
Any new medications or changes in medications since last visit?		
If Yes, please add medication(s) to the Concomitant Medication form. Acute abortive medications and migraine prophylactic medications should not be changed during the clinical trial.		

Subject Compliance:	Yes	No
Is the subject compliant with daily device treatments?		
Is the subject compliant with Daily Headache Diary and uploads?		
If No, to any questions above, please provide comment:		

- Review device compliance and proper operation of the device and delivery of treatments.
- Review Daily Headache Diary completion and upload to gmail account each day.

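### Mandatory withdrawal for significant non-compliance can cost some randomised subjects the primary outcome that the intent-to-treat analysis needs

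*Combined protocol and SAP*

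**What the plan says.** All references are to the combined protocol and SAP.

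- **Section 2, Withdrawal Criteria.** The list opens with "Subjects must be withdrawn from the clinical trial if any of the following events occur" and includes "A subject is significantly non-compliant with the requirements of the protocol (principal investigator & sponsor decision". It sets no threshold for significant, covers protocol requirements in general and not device use alone, and has no time limit. The diary line that follows it is confined to the baseline period.
- **Section 2, after discontinuation.** The investigator is to try to obtain the final-visit evaluations and to record the reason. Continued diary entry is not mentioned, and the Early Termination Visit form has no diary item.
- **Section 8, analysis sets.** "An intent-to-treat methodology will be employed for the primary aim; however, per protocol analyses will also be conducted for comparison" Compliance, for the per-protocol evaluation, means at least 50% in each treatment month, and "Subjects with treatment compliance below 50% during any treatment month will be assigned to the intent-to-treat group only".
- **Section 8, data needed.** The analysis of the primary endpoint "will be performed for all subjects that complete at least 25 diary entries or more during the relevant 28-day treatment month". No method is given for a missing month 3.
- **Section 3.** The target of up to 120 counts subjects who complete the first treatment period. Section 7 ties the analysis to 120 reaching that point.

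**The concern.** Each provision is reasonable alone, but nothing says how they fit together. Section 8 expects poor users of the device to stay in the intent-to-treat set. Section 2 gives the investigator and sponsor a mandatory but undefined ground for ending the participation of some of the same people after randomisation.

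Poor device use is a post-randomisation event and may depend on treatment. Section 6 lists dizziness, drowsiness and vertigo among the more likely effects, and section 5 leaves the placebo earpieces unpowered. Reasons for stopping use, and so the chance of withdrawal, may differ between arms. If those subjects drop out of the primary comparison, it is no longer fully protected by randomisation, and the planned check of intent-to-treat against per-protocol becomes less informative.

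**Working it through.** **1. The plan's own figure.** Section 8 gives 40 per arm, SD 3.36, α = 0.05, 80% power and a detectable difference of 2.13 days. Sidedness is not stated; two-sided is assumed. The normal approximation gives (1.960 + 0.842) × 3.36 × √(2/40) = 2.10 days. The t-test gives 2.13 days, with power 0.7995 at that value. The figure reproduces, so no stated number is wrong on this point.

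**2. From withdrawal to a lost outcome.** Baseline is weeks 1–4 and the first treatment period weeks 5–16, so month 3 is weeks 13–16. Device compliance is reviewed at the Day 14 visit (week 7) and at phone contacts in weeks 9, 11, 13 and 15. The SD-card log is extracted at the end of week 16.

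- A subject withdrawn around the week 9 or 11 contact has no month-3 entries.
- The 25-entry rule tolerates 28 − 25 = 3 missing days. A diary that stops with more than three days of month 3 left fails it.
- Only final-visit evaluations are then sought, so the outcome is not recovered.
- The target counts completers, so a withdrawn subject does not count towards 120. If 40 completers per arm are still reached, the problem is selection and not power.

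**3. Size (upper illustration).** The Background gives first-trial reductions of 3.6 days (active) and 0.9 days (placebo). Let p be the share of the twice-daily active arm that is non-compliant. Assume that all of these are withdrawn, that they respond like placebo, that nobody is withdrawn from placebo, and that 3.6 is the mean among compliers.

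- Everyone kept: 3.6(1 − p) + 0.9p − 0.9 = 2.7(1 − p)
- Non-compliers removed: 3.6 − 0.9 = 2.7
- Overstatement: 2.7p

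| p (assumed) | Kept | Removed | Overstated by |
|---|---|---|---|
| 5% | 2.57 | 2.70 | 0.14 |
| 10% | 2.43 | 2.70 | 0.27 |
| 12.5% | 2.36 | 2.70 | 0.34 |

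The last row equals 5/40, the dropout that section 8 expects from all causes in each three-month period. Using section 8's first-trial figure of 2.73 gives the same overstatement to two decimals: 0.14, 0.27 and 0.34.

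**4. Direction.** Suppose instead that 12.5% of placebo subjects are withdrawn and that they had no mean reduction (an assumption). The remaining placebo mean becomes 0.9/(1 − 0.125) = 1.03, which lowers the difference by 0.13 days. If only placebo subjects were withdrawn, the difference would be understated by that amount. With 12.5% withdrawn from both arms, it is 3.6 − 1.03 = 2.57 against 2.36 with everyone kept, an overstatement of 0.21.

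**5. Power if everyone is kept.** With 40 per arm, SD 3.36 and a complier effect of 2.73 days, t-test power is 0.948 with no non-compliers. It is 0.898 at 10% (difference 2.46), 0.881 at 12.5% (2.39) and 0.819 at 20% (2.18).

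**The case against.** The strongest defence is that the two rules operate at different levels. Section 8 is the specific rule for device use and tolerates ordinary under-use. Section 2 is a reserve power for serious breaches of any kind, and it withdraws a subject from the trial without deleting anyone from an analysis set. Much of this stands: the withdrawal line is not tied to 50%, and section 8 plainly expects some subjects below that level to remain. It does not answer the point that a withdrawn subject's diary would normally stop and that the 25-entry rule would then exclude that subject.

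The documents do not support four stronger readings that a reader might infer:

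- **That intent-to-treat becomes a second per-protocol analysis.** The rule is discretionary and can remove some non-compliers. Subjects below 50% by SD card are identified after week 16, when their month-3 diaries exist.
- **That self-report by phone is the only compliance information in the first period.** At the Day 14 visit the subject brings the device and treats in front of the coordinator, and the form calls for a review of device compliance. Only the SD-card log comes later.
- **That the sponsor could use unblinding card data to decide who leaves the primary analysis.** The Visit 4 form says "Collect and return old Treatment card (SD card) from the device to Scion NeuroStim (SNS", and the cards hold "temperature waveform files that contain actual measured temperature values that were delivered to the earpieces during treatments". That visit is at the end of week 16, too late to affect month-3 data. The point could bear only on later periods.
- **That the bias may reach 0.54 days.** That needs p = 20%, above the protocol's expected dropout from all causes.

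**Conclusion.** The point holds as a gap that should be closed. Followed as written, the withdrawal line, the final-visit-only follow-up and the 25-entry rule together can remove some non-compliant randomised subjects from the primary comparison, despite its intent-to-treat label. The loss may differ by arm.

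On the upper illustration the overstatement is 0.27 days at 10% and 0.34 days at 12.5%, against a difference of 2.7. This rests on an assumed non-compliance rate, complete withdrawal of active-arm non-compliers, a placebo-like response in them and no placebo withdrawals. The real effect could be smaller, and its direction is not established if placebo subjects are also withdrawn. The power calculation is not in question.

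**What to change.** Reconcile the withdrawal list and discontinuation text in section 2, the completer-based target in section 3 and the analysis rules in section 8, so that for randomised subjects non-compliance by itself does not end outcome collection:

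- Continue the daily diary and phone contacts through month 3, unless consent is withdrawn.
- Include those diaries in the intent-to-treat analysis, and state how a randomised subject with fewer than 25 month-3 entries is handled.
- Let the SD-card 50% rule alone decide per-protocol membership with respect to device use.
- Say what significant non-compliance means and how such subjects count towards the 120.

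Section 2 already does something similar: subjects who exceed 14 headache days in a treatment month stay in the study and are followed. The change concerns outcome collection only. Decisions on stopping device treatment, and the safety, pregnancy and consent withdrawal lines, are untouched.

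The cost is a few lines of text, modest extra follow-up of a few poorly engaged subjects, and a possibly slightly less favourable estimate. On the assumptions above, power with everyone kept stays above 80% even at 20% non-compliance.
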